3.4 Randomization, Replacement, and Unblinding Procedures

Subjects will be randomized in a 1:1:1 ratio to one of the following treatment regimens:

- Part A: ASN002 40 mg (16-week treatment); Part B: ASN002 40 mg (16-week treatment)
- Part A: ASN002 80 mg (16-week treatment); Part B: ASN002 80 mg (16-week treatment)
- Part A: Placebo (16-week treatment); Part B: ASN002 80 mg (16-week treatment)

Subjects assigned to regimen starting with a placebo in Part A (first 16 weeks) of the study will receive the highest dose of ASN002 (i.e. 80 mg) for the rest of the treatment period (up to Week 32). Subjects who were assigned to ASN002 in the first part of the study will continue on the assigned treatment dose during the second part of the study up 32 weeks of treatment.

Randomization will occur prior to first dosing, at Day 1 visit. The randomization list will be generated using validated software. Randomization will be stratified for the biopsy collection and for the PGA score of '3' (moderate) or '4' (severe) per treatment group. The master randomization list will be kept secured until the study blind is broken. This list will be uploaded into an Interactive Web Response System (IWRS). The investigator or designee will be able to acquire a randomization number for eligible subjects by connecting to the IWRS

This study will be double-blinded. At all times, treatment and randomization information will be kept confidential and will not be released to, the contract research organization (CRO), or the sponsor's study team until database lock of Part A is completed and all safety data has been cleaned and monitored. Investigators, subjects and clinical staff will remain blinded throughout the study.

PPD	STATISTICAL ANALYSIS PLAN, Version Final 1.0
Protocol Number: ASN002AD-202 V6.0	Sponsor: Asana BioSciences, LLC

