5.1 Sample Size

Assuming a common standard deviation of 39% for the percent change-from-baseline mTLSS, a difference of 25% and 35% between the 40 mg dose vs. placebo and the 80 mg dose vs. placebo, respectively, alpha of 5% (two-sided), 25 patients per group would insure an 80% power to obtain a statistically significant treatment effect (using the general F test in an analysis of variance). Assuming between 25-30% dropout rates, up to 35 patients per group will be included in this study.

PPD	STATISTICAL ANALYSIS PLAN, Version Final 1.0
Protocol Number: ASN002AD-202 V6.0	Sponsor: Asana BioSciences, LLC

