6.2 Handling of Dropouts or Missing data

See Appendix 2 for handling of completely or partially missing dates for prior and concomitant medications and adverse events.

For safety analyses, no imputation of the data will be done and analyses will be conducted on the observed cases (OC). In Part A efficacy analyses will be performed using Mixed Model Repeated Measures (MMRM) analyses as primary analyses to account for missing observations (See section 13.1).

For subjects starting prohibited medications as listed in section 6.4.3 of the protocol, all efficacy data captured after the start of prohibited medication will be considered missing for the analysis of those parameters. A sensitivity analysis on the primary endpoint mTLSS will be done including all efficacy data for these subjects (before and after the prohibited medication).

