For categorical efficacy endpoints involving proportions hand PGA, a Cochran Mantel Hansel test (CMH) stratified by baseline PGA will be presented by visit for Part A. Analyses will be based on the mITT population for all secondary parameters and supported by the PP population. Missing data at any post-baseline assessment will be imputed as a non-responder.

Actual values of PaGA will summarized descriptively using frequency and percentage.

Time to response relative to baseline (based on hand PGA) will be compared between treatments using the Kaplan Meier method. A subject will be considered censored if he has not met the event of interest at the end of the study or if the subject is lost to follow up at last observation. Those subjects will be censored at their last available hand PGA assessment.

Descriptive statistics will be presented for all secondary endpoints by visit and treatment group and sorted by Part A.

All endpoints relative Part B for the above assessments are considered exploratory only and will be summarized descriptively by initial treatment group and overall.

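### Time to hand PGA response censors dropouts and, by inference, rescued subjects, so the Kaplan-Meier response rate exceeds the proportion who respond without dropout or rescue, and the treatment comparison can shift either way

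*SAP*

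**What the plan says.** SAP 13.2 defines the event for time to response as a hand PGA of 0 or 1 and compares treatments by Kaplan-Meier. It names two groups to be censored: subjects with no event when the study ends, and subjects lost to follow-up. The censoring time is then given: "Those subjects will be censored at their last available hand PGA assessment".

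For the hand PGA proportions, analysed by CMH, the same section gives a different rule: "Missing data at any post-baseline assessment will be imputed as a non-responder".

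Rescue enters through SAP 6.2. For subjects who start prohibited medication, "all efficacy data captured after the start of prohibited medication will be considered missing for the analysis of those parameters". Protocol 6.4.3 ties topical rescue to an exacerbation of the hand eczema. It lets subjects who start rescue after Week 8 remain under assessment, and it takes those who start earlier off study product.

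Two sections disagree on the time horizon. The secondary endpoint analyses in SAP 13.2 are based on Part A, with time to PGA response as the stated exception. SAP 3.5 limits all secondary efficacy endpoints to Week 16 and treats later data as exploratory. Placebo subjects switch to ASN002 80 mg at Week 16.

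**The concern.** Kaplan-Meier treats a censored subject as having the same future chance of response as subjects still at risk. That is hard to defend for someone who withdrew because the eczema worsened or who needed rescue for an exacerbation. The protocol expects withdrawal for worsening often enough to list it as an endpoint at Weeks 4, 8, 12 and 16, and the plan allows for 25-30% dropout.

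The same section counts these subjects as failures in one hand PGA analysis and removes them from the denominator in the other. A reader of the Kaplan-Meier curve would see a higher response rate than the share of treated subjects who responded without dropping out or being rescued. No sensitivity analysis covers this endpoint. The only one for prohibited medication concerns mTLSS.

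**Working it through.** **The plan's own figures.** The documents give no number for time to response. The dropout figure comes from SAP 5.1, so I checked that calculation first. Its inputs are an SD of 39 points, effects against placebo of 25 points (40 mg) and 35 points (80 mg), a two-sided 5% level, and 25 per group for 80% power. The test is given as "using the general F test in an analysis of variance". Allocation is 1:1:1 (SAP 3.4).

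- Means 0, 25 and 35 have average 20. The squared deviations sum to 400 + 25 + 225 = 650.
- Noncentrality = n × 650 / 39² = 25 × 650 / 1521 = 10.68, with 2 and 72 degrees of freedom. Power is 82.5%. At n = 24 it is 80.8%.
- Dropout: 25/0.75 = 33.3 (34) and 25/0.70 = 35.7 (36). The planned 35 implies 1 − 25/35 = 28.6%.

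The stated size reproduces, and 25-30% is the plan's own dropout range. It is not given by arm, and it need not equal the share who drop out or are rescued before responding.

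**The two estimators.** The model uses the five post-baseline PGA visits of Part A (Weeks 2, 4, 8, 12 and 16). Let h be the chance of response at a visit among those still at risk, and d the chance of failing (dropout or rescue) just before a visit. Both are constant over visits.

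- Failures censored: Kaplan-Meier response = 1 − (1 − h)^5.
- Failures kept as non-responders: response = sum over visits of (fraction at risk × h). Each visit first removes the fraction d and then the responders.

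The first is never smaller than the second, because censoring takes failures out of the denominator.

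**One case in full.** Assume 20% respond by Week 16 with failures counted as non-responders, and 25% fail before responding. Solving gives d = 0.0626 and h = 0.0534.

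| Visit | Cumulative failures | Cumulative response | Still at risk |
|---|---|---|---|
| Week 2 | 6.3% | 5.0% | 88.7% |
| Week 4 | 11.8% | 9.5% | 78.7% |
| Week 8 | 16.8% | 13.4% | 69.9% |
| Week 12 | 21.1% | 16.9% | 62.0% |
| Week 16 | 25.0% | 20.0% | 55.0% |

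Kaplan-Meier gives 1 − (1 − 0.0534)^5 = 24.0%, which is 1.20 times 20%.

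**Other assumed response rates at the planned dropout range.**

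| Response, failures as non-responders | Kaplan-Meier, 25% failing | Kaplan-Meier, 30% failing |
|---|---|---|
| 10% | 11.9% | 12.4% |
| 20% | 24.0% | 25.1% |
| 40% | 48.9% | 51.5% |

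For response between 5% and 50%, the ratio runs from 1.19 to 1.31.

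**Effect on the comparison.**

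- Equal response of 20%, with 20% failing in one arm and 40% in the other: Kaplan-Meier gives 23.0% and 27.7%. The arm with more failures gains more (+7.7 against +3.0 points).
- Placebo 10% response with 40% failing; active 40% response with 25% failing: Kaplan-Meier gives 13.6% (+3.6 points, ×1.36) and 48.9% (+8.9 points, ×1.22). The arm difference grows from 30.0 to 35.3 points, while the ratio falls from 4.0 to 48.9/13.6 = 3.6.

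**A second model.** This one uses rising response chances at Weeks 4, 8, 12 and 16: 3/5/7/8% on placebo and 8/12/15/15% on active. The chances of leaving before each visit are 4/6/6/6% on active (20% compounded), and on placebo either 8/15/15/12% (42%) or 5/10/10/10% (31%).

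| Case | Placebo: failures counted → Kaplan-Meier | Active: failures counted → Kaplan-Meier | Arm difference |
|---|---|---|---|
| Placebo 42% | 14.9% → 21.2% | 36.2% → 41.5% | 21.3 → 20.3 points |
| Placebo 31% | 16.7% → 21.2% | 36.2% → 41.5% | 19.5 → 20.4 points |

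The arm difference narrows in one case and widens in the other. If leaving follows the visit instead, the 42% case starts from 17.1% and 38.3%, so the excess shrinks to 4.1 and 3.2 points but remains.

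**The case against.** **The SAP does not say that rescued subjects are censored.** Correct. SAP 13.2 names only the end of the study and loss to follow-up. The rescue route comes from reading 6.2 and 13.2 together. No other rule for rescued subjects is given, so the inference is reasonable, and the silence is itself a gap.

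**Censoring may be valid for another target.** If the aim were response had nobody dropped out or been rescued, and censoring were independent, Kaplan-Meier would not be biased. The SAP states no target. Overstatement is therefore relative to counting failures as non-responders, which is the SAP's own rule for the PGA proportions. Rescue for exacerbation also makes independence doubtful.

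**A reader might infer that the arm with most failures is always inflated most, so the benefit of ASN002 is understated.** The documents do not support that. It holds on the ratio scale in these examples, or at equal response rates. In absolute points the arm with the higher response rate can gain more, as shown above.

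**A reader might also infer that correcting the censoring makes the Week 16 value equal the CMH proportion.** It need not. Time to response counts a first response at any visit, while the CMH counts status at the visit. A subject clear at Week 8 who has relapsed by Week 16 is an event in one and a non-responder in the other.

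**The stakes are limited.** True. SAP 6.5 makes secondary p-values nominal, and dropouts already count as failures in the PGA proportions.

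**Conclusion.** The point holds in this form: two rules for failures on hand PGA sit in one section, and the time-to-response rule gives a response rate above the proportion who respond without dropout or rescue. That excess follows from the estimator whenever subjects leave the risk set before a later response is counted. Its size rests on assumed rates: about 1.2 to 1.3 times with 25-30% failing before response, if the planned dropout range is a fair guide to failures. The documents give no rates by arm, so the effect on the treatment comparison cannot be signed.

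This is a worthwhile correction to a secondary endpoint. It does not affect the primary endpoint or the sample size.

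**What to change.** In SAP 13.2:

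1. State the target of the time-to-response analysis.
2. For the main analysis, keep subjects who withdraw or start prohibited eczema therapy before responding in the risk set as non-responders to the end of the analysis period. Equivalently, report cumulative incidence with withdrawal or rescue as a competing event. Present it by arm and account for the baseline PGA stratum. Name rescue explicitly.
3. Show the current censoring as a sensitivity analysis.
4. Set the analysis period by reconciling the Part A exception in 13.2 with the Week 16 limit in 3.5. Without this, responses of placebo subjects after their switch to ASN002 could count in the placebo curve.
5. Note that failure handling then agrees with the CMH, but that the Week 16 values may still differ.

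Protocol 6.4.3 and 7.1 also differ on whether a subject given another effective therapy stays in the study, and they must be reconciled. The analysis rule above gives the same result either way.

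The cost is a few sentences and minor programming, before unblinding. The downside is that subjects lost for unrelated reasons count as non-responders, as they already do in the CMH.

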13.3 Exploratory Endpoints

Chronic Eczema Subtype Analysis

Subgroup analysis using descriptive statistics by baseline description of CHE (hyperkeratotic, fingertip or pompholyx) will be performed using the primary endpoint - percent change in mTLSS.

Subgroup analysis using descriptive statistics by baseline description of CHE will also be performed for the PGA response outcome as defined in Section 13.2.

Pruritus NRS section of hand mTLSS

PPD	STATISTICAL ANALYSIS PLAN, Version Final 1.0
Protocol Number: ASN002AD-202 V6.0	Sponsor: Asana BioSciences, LLC

The pruritus/pain parameter score of the hand mTLSS questionnaire will be analyzed using descriptive statistics.

Work Productivity and Activity Impairment Measure: Specific Health Problem

The work productivity and activity impairment: specific health problem (WPAI:SHP) measure will be assessed at the visits specified in [Table 1](#), and evaluated for CHE. It is a simple 6-question validated questionnaire that has been used for different health conditions and customized by replacing the word PROBLEM of the questionnaire by the condition that is studied. Its use has been described in many publications, including many multinational studies.

The WPAI-SHP allows us to calculate four scores (multiply by 100 for percent):

Percent work time missed due to CHE: $Q2/(Q2+Q4)$

Percent impairment while working due to CHE: $Q5/10$

Percent overall work impairment due to CHE: $Q2/(Q2+Q3) + \{(1-(Q2)/(Q2+Q3)) \times Q5/10\}$

Percent activity impairment due to CHE: $Q6/10$

Where variables Q1-Q6 are the questions from WPAI-SHP:

Questions:

- 1 = currently employed
- 2 = hours missed due to CHE
- 3 = hours missed other reasons
- 4 = hours actually worked
- 5 = degree CHE affected productivity while working
- 6 = degree CHE affected regular activities

WPAI-SHP scores will be analyzed as follows:

- Change from baseline in Work Productivity and Activity Impairment – Specific Health Problem (WPAI-SHP) questionnaire at all visits with assessments scheduled from Weeks 4 to Week 32 for each domain
- Proportion of patients with 20% or higher impairment in Work Productivity and Activity Impairment – Specific Health Problem (WPAI-SHP) questionnaire at all visits with assessments scheduled from Weeks 4 to Week 32 for each domain

PPD	STATISTICAL ANALYSIS PLAN, Version Final 1.0
Protocol Number: ASN002AD-202 V6.0	Sponsor: Asana BioSciences, LLC

Extent of Disease

Extent of disease will be assessed at the visits specified in [Table 1](#) and will be estimated by the physician as the percentage of hand area (palmar and dorsal) affected by eczema, both hands (both surface) cumulating 100%.

Extend of Disease will be analyzed as follows:

- Change and percent change from baseline in Extent of Disease affected with moderate to severe CHE at all visits with assessments scheduled

Modified Total Lesion Symptom Score (mTLSS) Feet

For exploratory purposes, a separate mTLSS will be evaluated for the feet for subjects for which the presence of foot eczema will be documented at the screening and Day 1 visits. Scores will be assigned for the most affected side (plantar or dorsal) of the most affected foot. Only subjects with foot involvement at baseline will be part of these analyses.

Foot mTLSS will be analyzed as follows:

- Change and percent change from baseline in foot mTLSS at all visits with assessments scheduled from Weeks 4 to Week 32

Physician's Global Assessment (PGA) Feet

For exploratory purposes, a separate PGA will be evaluated for the feet, for subjects for which the presence of foot eczema will be documented at the screening and Day 1 visits. Only subjects with foot involvement at baseline will be part of these analyses.

Foot PGA will be analyzed as follows:

- Proportion of subjects achieving at least a 2-grade reduction from baseline to clear (0), almost clear (1) or mild (2) in foot PGA at all visits with assessments scheduled from Weeks 4 to Week 32
- Proportion of subjects achieving a foot PGA of clear (0) or almost clear (1) at all visits with assessments scheduled from Weeks 4 to Week 32
- Change from baseline in foot PGA at all visits with assessments scheduled from Weeks 4 to Week 32

Extent of Disease for Subjects Affected with Foot Eczema

PPD	STATISTICAL ANALYSIS PLAN, Version Final 1.0
Protocol Number: ASN002AD-202 V6.0	Sponsor: Asana BioSciences, LLC

Presence or absence of foot eczema will be assessed at the visits specified in [Table 1](#) must be documented in the source document and eCRF. For exploratory purposes, a separate extent of the disease will be evaluated for the feet, for subjects for which the presence of foot eczema will be documented at the visits specified in [Table 1](#). Percentage will be estimated by the physician as the percentage of foot area (plantar and dorsal) affected by eczema, both feet (both surface) cumulating 100%. Only subjects with foot involvement at baseline will be part of these analyses.

Analyzes will be done as follows:

- Change and percent change from baseline in Extent of Disease affected with foot eczema at all visits with assessments scheduled from Weeks 4 to Week 32

Validated Investigator Global Assessment (for Subjects with AD only)

For subjects with AD only, disease severity (excluding hands and feet) will be assessed at the visits specified in **Error! Reference source not found.**, before the study product administration, using the validated Investigator Global Assessment scale for atopic dermatitis (vIGA-AD). The vIGA is a global assessment of the current state of the disease. It is a 5-point morphological assessment of overall disease severity. The condition will be documented in the eCRF along with the vIGA scores recorded at the visits specified in Table 1.

Analyzes will be done using:

- Proportion of subjects achieving at least a 2-grade reduction from baseline to clear (0) or almost clear (1) in vIGA at Weeks 4 and 16.
- Proportion of subjects achieving at least a 2-grade reduction from baseline in vIGA at Weeks 4 and 16.
- Change from baseline in vIGA at Weeks 4 and 16

Exploratory Analysis

Change and/or percent change in hand mTLSS by CHE subtype, pruritus score portion of mTLSS, WPAI-SHP, Extent of Disease, foot mTLSS and foot PGA will be presented using descriptive statistics by visit and initial treatment group for both parts of the study. Analyses will be based on the mITT population.

PPD	STATISTICAL ANALYSIS PLAN, Version Final 1.0
Protocol Number: ASN002AD-202 V6.0	Sponsor: Asana BioSciences, LLC

For categorical efficacy endpoints involving proportions based on foot PGA and vIGA, counts and percentages will be presented for each visit.

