APPENDIX A: Work Productivity and Activity Impairment Questionnaire (WPAI-SHP:CHE)

Subject ID #: _____	-	Subject Initials: _____
Visit: _____	Visit Date (dd-mmm-yyyy): _____	
Section to be completed by site staff		

Work Productivity and Activity Impairment Questionnaire: Specific Health Problem V2.0 (WPAI:SHP:CHE)

The following questions ask about the effect of your *CHRONIC HAND ECZEMA* on your ability to work and perform regular activities. *Please fill in the blanks or circle a number, as indicated.*

1. Are you currently employed (working for pay)? _____ NO _____ YES
If NO, check “NO” and skip to question 6.

The next questions are about the **past seven days**, not including today.

2. During the past seven days, how many hours did you miss from work because of problems associated with your CHRONIC HAND ECZEMA? *Include hours you missed on sick days, times you went in late, left early, etc., because of your CHRONIC HAND ECZEMA. Do not include time you missed to participate in this study.*

_____ HOURS

3. During the past seven days, how many hours did you miss from work because of any other reason, such as vacation, holidays, time off to participate in this study?

_____ HOURS

[figure not shown]
4. During the past seven days, how many hours did you actually work?

_____ HOURS *(If “0”, skip to question 6.)*

5. During the past seven days, how much did your CHRONIC HAND ECZEMA affect your productivity while you were working?

Think about days you were limited in the amount or kind of work you could do, days you accomplished less than you would like, or days you could not do your work as carefully as usual. If CHRONIC HAND ECZEMA affected your work only a little, choose a low number. Choose a high number if CHRONIC HAND ECZEMA affected your work a great deal.

Consider only how much CHRONIC HAND ECZEMA affected productivity while you were working.

[figure not shown]

CIRCLE A NUMBER

6. During the past seven days, how much did your CHRONIC HAND ECZEMA affect your ability to do your regular daily activities, other than work at a job?

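### The SAP's WPAI overall work impairment formula divides by hours missed for other reasons (Q3) instead of hours worked (Q4), so it is undefined or 100% whenever Q3 is zero

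*SAP*

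**What the plan says.** SAP Section 13.3, in the part on work productivity, lists four WPAI scores. The first is "Percent work time missed due to CHE: $Q2/(Q2+Q4", closing bracket to follow, so its denominator is hours missed for CHE plus hours worked. The second is "Percent impairment while working due to CHE: $Q5/10". The third begins "Percent overall work impairment due to CHE: $Q2/(Q2+Q3" and then adds one minus that same fraction, multiplied by Q5/10. Q3 stands in both denominators and Q4 appears in neither. The fourth, activity impairment, uses only Q6.

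The item key below the formulas reads "2 = hours missed due to CHE", "3 = hours missed other reasons" and "4 = hours actually worked". The questionnaire in Protocol Appendix A agrees. Its third question asks "how many hours did you miss from work because of any other reason, such as vacation, holidays, time off to participate in this study", and its fourth asks "During the past seven days, how many hours did you actually work".

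The SAP then plans two summaries of each score from Week 4 to Week 32: the change from baseline, and the proportion of patients at or above 20% impairment.

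**The concern.** Overall work impairment combines two losses: the share of working time lost to CHE, and reduced productivity during the time still worked. The first term should therefore be the work-time-missed share that the SAP has already defined. The weight on Q5/10 should be the share of time worked, because Q5 rates productivity at work. As printed, that weight is Q3/(Q2+Q3), so on-the-job impairment is weighted by vacation and other absence, and hours worked never enter the score.

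At stake is the only WPAI score that combines absence with impairment at work. Undefined values would remove subjects from the summaries, and an undefined baseline would remove a subject's change score at every later visit. The 100% values would hide real improvement.

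**Working it through.** The documents give no numerical result for this score, so there is no figure to reproduce. The check evaluates the printed formula beside the same formula with Q4 in place of Q3.

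**Inputs.** The formulas and item meanings come from SAP Section 13.3 and Protocol Appendix A. The answers below are invented examples that assume a 40-hour week (Q2+Q3+Q4 = 40).

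**Formulas.** Let p = Q5/10 and let w be the time-missed share. The score is w + (1 − w)p = p + w(1 − p).

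- As printed: w = Q2/(Q2+Q3)
- With hours worked: w = Q2/(Q2+Q4)

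**General results for the printed version.**

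- Q2 = 0 and Q3 = 0: w = 0/0, so the score is undefined whatever Q4 and Q5 are.
- Q2 > 0 and Q3 = 0: w = 1, so the score is p + (1 − p) = 100% whatever Q4 and Q5 are.
- Q2 > 0 and Q3 > 0: the error is (1 − p) × [Q2/(Q2+Q3) − Q2/(Q2+Q4)]. The score is too high when Q3 < Q4 and too low when Q3 > Q4, unless p = 1.
- The versions agree when Q2 = 0 with Q3 > 0 and Q4 > 0 (both equal p), when Q3 = Q4, or when Q5 = 10, provided the denominators are not zero.

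**Examples.**

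| Q2 | Q3 | Q4 | Q5 | As printed | With Q4 |
|---|---|---|---|---|---|
| 0 | 0 | 40 | 3 | undefined | 30% |
| 1 | 0 | 39 | 0 | 100% | 2.5% |
| 1 | 0 | 39 | 1 | 100% | 12.25% |
| 4 | 0 | 36 | 3 | 100% | 37% |
| 2 | 2 | 36 | 2 | 60% | 24.2% |
| 4 | 8 | 28 | 3 | 53.3% | 38.75% |
| 8 | 8 | 24 | 3 | 65% | 47.5% |
| 0 | 8 | 32 | 5 | 50% | 50% |

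For the fourth row, with Q4: w = 4/40 = 0.10 and 0.10 + 0.90 × 0.3 = 0.37. As printed: w = 4/4 = 1 and 1 + 0 × 0.3 = 1.

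**Effect on the planned summaries.**

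- *Change from baseline.* Take a subject who goes from (Q2, Q3, Q4, Q5) = (4, 0, 36, 8) to (1, 0, 39, 0). With Q4 the score falls from 0.10 + 0.90 × 0.8 = 82% to 2.5%, a drop of 79.5 points. As printed it is 100% both times, a change of zero. If the subject improves further to Q2 = 0 with Q3 still 0, the score becomes undefined, so missing values are tied to benefit.
- *20% threshold.* The third row counts as impaired as printed (100%) but not with Q4 (12.25%). The first row, at 30%, should count but cannot, because it has no value.

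**The case against.** The strongest reply concerns reach. WPAI is exploratory and the SAP presents it with descriptive statistics only. No primary, secondary or safety result uses this formula, and the Hochberg procedure does not touch it. Three of the four scores do not involve Q3, so both components of the overall score are still reported correctly and the work-productivity objective is only partly affected. The score applies only to employed subjects, since the questionnaire sends the others straight to question 6. The extreme results need Q3 = 0, and the documents do not say how often that occurs. All of this stands, and it limits the consequence.

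It does not rescue the formula. A text-extraction fault is unlikely, because Q3 appears in both denominators while Q4 is read correctly two lines above. SAP Section 3.5 lists the changes from the protocol and none concerns WPAI scoring. Neither document gives another formula or a rule for a zero denominator. Assuming that the programmer would follow published scoring instead would rest on a source outside the plan.

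It is also fair to say that swapping the item does not settle every case. Q2 = Q4 = 0 still gives 0/0, and a subject with Q4 = 0 is told to skip Q5.

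**Conclusion.** The formula is wrong as written, and the SAP's own item key and work-time-missed formula are enough to show it. For every employed subject with Q3 = 0, the printed score is either undefined or exactly 100%. In the examples with hours missed for both reasons (Q2 and Q3 above zero), it is too high by about 15 to 36 points (53.3 against 38.75; 60 against 24.2).

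The example hours assume a 40-hour week, but the undefined and 100% results do not depend on that. That Q3 = 0 is a common answer is an assumption, though a modest one: it needs only a week without vacation, holiday or other non-CHE absence. The error must be corrected before this score is derived. It does not threaten the primary or secondary results.

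**What to change.** In SAP Section 13.3, replace the overall work impairment formula with

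Q2/(Q2+Q4) + {(1 − Q2/(Q2+Q4)) × Q5/10}

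and check that the derivation program matches. Add a sentence for subjects who worked no hours. For example, set the score to missing when Q2 = Q4 = 0. When Q4 = 0 and Q2 > 0, set it to 100%, because the skipped Q5 then carries zero weight. The work-time-missed score needs the same rule for Q2 = Q4 = 0.

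The cost is one corrected line, one added sentence and one derivation. All items are already collected, so nothing changes in the questionnaire or trial conduct. SAP Section 1 places the plan before database lock and final unblinding, so a correction at that stage raises no question of data-driven change.
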